4.1 Primary Objective

The primary objective of this study is to assess circulating cannabinoid levels and safety of CBD administered to patients with AUD at doses calculated to yield circulating CBD levels comparable to those that produced clinically relevant effects in animal models of AUD. We predict that within-group circulating CBD levels will stabilize within one week (i.e. pre-CBD dosing levels obtained after 1 week of treatment will not differ from those obtained after 4 weeks of treatment at each dose), that circulating CBD levels obtained at the 1200 mg/day dose will be comparable to those associated with anti-addictive effects in animal models, (i.e., in the range of 200-400 ng/ml), and that no clinically significant cognitive or motoric impairments, CBD-related serious adverse events, or persisting adverse effects will be observed.

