7.3.1 Administration of Intervention

CBD (or placebo) will be administered daily for 8 weeks. The first administration of each dose of CBD vs. placebo (at T1 and T4) will take place at the study site. Participants will remain at the study site with a study team member for approximately 2 hours following the initial administration of each dose of CBD, and participants will not be permitted to leave the study site until they are able to pass a standard field sobriety test (a walk-and-turn task, one-leg stand, Romberg's test, finger-finger test, and counting backwards [97]). If there are no AEs during this time period or lasting intoxicating effects of the study drug (i.e. participants are able to pass field sobriety tests 2-3 hours after study drug administration), participants will be dispensed the proper quantity of study drug (CBD or placebo) to self-administer daily at home until the next scheduled study visit (i.e. a 1- or 3-week supply, depending on the visit).

CONFIDENTIAL

This material is the property of the NYU School of Medicine and Langone Health
Do not disclose or use except as authorized in writing by the study sponsor

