21.2 Statistical Hypotheses

Hypothesis 1a: Within-group circulating CBD levels will stabilize within one week, i.e. pre-CBD dosing (12 hour) levels obtained after 1 week of treatment will not differ from those obtained after 4 weeks of treatment at each dose.

Hypothesis 1b: Circulating CBD levels obtained at the 1200 mg/day dose will be comparable to those associated with anti-additive effects in animal models, i.e., in the range of 200-400 ng/ml.

Hypothesis 1c: No clinically significant cognitive or motoric impairments, CBD-related serious adverse events, or persisting adverse effects will be observed.

Hypothesis 2a: Relative to placebo, CBD will improve self-report measures of craving, anxiety, mood, and self-efficacy.

Hypothesis 2b: Relative to placebo, CBD will be associated with decreased stress- and alcohol cue-induced craving and physiological stress response

Hypothesis E: Relative to the placebo-treated group, CBD-treated participants will have fewer heavy drinking days during and for four weeks after treatment with 1200mg/day CBD vs. placebo.

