21.3 Description of Statistical Methods

21.3.1 General Approach

The distributional characteristics of the measures used to investigate the aims of the study will be assessed and data transformations will be explored if necessary. For all hypotheses, linear mixed effects models will be constructed including treatment group as a fixed between-subjects factor, time (T0-T9) as a fixed within-subjects factor, and subject as a random effect. Treatment groups will also be compared on baseline measures of alcohol consumption (% drinking days and % heavy drinking days), alcohol craving (PACS), anxiety (BAI), mood (BDI-II), and self-efficacy (AASE), and baseline scores on these measures will be utilized as covariates for hypothesis evaluation.

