21.3.4 Safety Analyses

Means and standard deviations of acute circulating CBD and THC levels within CBD-treated participants 45 minutes after initial administration (T1, T4), and 45 minutes after administration of the morning dose of medication following 1 day (T2, T5), 1 week (T3, T6), and 4 weeks (T4, T7) of treatment with each dose of CBD will be assessed to determine whether target circulating levels of CBD have been achieved, and whether metabolic transformation of CBD to THC has occurred.

Means and standard deviations of change in 12 hour circulating CBD levels from 1 week to 4 weeks of treatment (T3 to T4, and T6 to T7) within CBD-treated participants will be presented to determine whether extended treatment with CBD results in accumulation of CBD.

The number of participants within each treatment group that were able to pass a battery of psychomotor field sobriety tasks (walk-and-turn task, one-leg stand, Romberg's test, finger-finger test, and counting backwards [97]) within 2 hours of the initial administration of each dose of CBD vs. placebo (T1 and T4) will be analyzed as summary statistics during treatment.

AEs and SAEs, when present, will be collected on an AE Case Report Form at study visits. The form will include an assessment of clinical significance and study relatedness. Serious Adverse Events (SAEs) will be documented on an additional SAE form. These CRFs will be based on those used in recent NIDA Clinical Trials Network trials. To further assess abuse potential, visual analog scales will be used to assess abuse potential. Scales will include desire to use the study medication again, desire to use the study medication again for pleasurable intoxication ("to get high"), and craving for the study medication.

The study may be stopped if there are untoward and concerning levels of Adverse Event (AE) or Serious Adverse Event (SAE) outcomes attributable to CBD or study participation. If the DSMB finds it is likely that CBD is contributing to negative outcomes, they will consider solutions including protocol changes or potentially stopping the study.

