21.3.8 Multiple Comparison/Multiplicity

Because our primary outcomes are safety data, in which we hypothesize a null difference between treatment groups, we will not employ a correction for Type I error/alpha inflation.

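### Hypotheses 1a and 1c (psychomotor and cognitive part) predict no difference, but no interval is planned, and at about 20 per arm a null result or small mean change cannot support them

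*Combined protocol and SAP*

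**What the plan says.** Section 21.2 states 1a as a within-arm prediction: 12-hour "levels obtained after 1 week of treatment will not differ from those obtained after 4 weeks of treatment at each dose". Section 4.1 predicts that "no clinically significant cognitive or motoric impairments, CBD-related serious adverse events, or persisting adverse effects will be observed", and 21.2 repeats this as 1c. For the comparison of arms, section 21.3.8 adds the framing "Because our primary outcomes are safety data, in which we hypothesize a null difference between treatment groups". That sentence concerns 1c only, since 1a compares visits inside the CBD arm.

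The planned evidence is as follows.
- Section 21.3.1: "For all hypotheses, linear mixed effects models will be constructed including treatment group as a fixed between-subjects factor".
- Section 21.3.2: CBD levels as mean and SD with effects of dose and timepoint; for 1c, group differences on psychomotor tasks (T1-T8) and cognitive measures (T3, T6).
- Section 21.3.4, for 1a: "Means and standard deviations of change in 12 hour circulating CBD levels from 1 week to 4 weeks of treatment" (T3 to T4, T6 to T7) "within CBD-treated participants will be presented to determine whether extended treatment with CBD results in accumulation of CBD".
- Section 21.3.4, for field sobriety: numbers passing at T1 and T4, which "will be analyzed as summary statistics during treatment".
- Section 21.4: sensitivity to detect differences, given as d of about 0.2 for 1a and 1c at power 0.95.

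Section 7.1.9 limits the primary analyses to participants who complete treatment through T7. Section 21.1 defers a formal SAP to a date before database lock and unblinding.

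**The concern.** A prediction of no difference cannot be supported by failing to find one, or by a small mean change shown without its uncertainty. What supports it is an interval showing how large a rise or impairment the data still allow. The plan has tools for detecting differences and for describing averages, but no planned interval and no statement of how a null result will be interpreted. Section 21.3.4 nevertheless means to reach a conclusion on accumulation from a mean and an SD.

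These are conclusions under the primary objective. If a non-significant or small average change were reported as no accumulation or no impairment, the claim could rest on data that are also compatible with a material rise or deficit.

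**Working it through.** **Inputs from the protocol.** 40 randomised 1:1 (section 5.1), so 20 per arm at best; 1a uses the CBD arm only. Alpha 0.05 and power 0.95 (section 21.4); sidedness is not stated. No SD, CV or dropout rate is given.

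**Assumptions.** True 25% rise in the 12-hour level; within-person CV 30%, 50% or 80%; true d = 0.5 for 1c; correlation between visits 0.5 to 0.7.

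**1. The plan's own figure.** Two groups of 20, d = 0.2: noncentrality = 0.2 × √(20/2) = 0.63, so the t-test has power of about 9% two-sided (15% one-sided), not 95%. Power 0.95 needs 2(1.960 + 1.645)²/0.2² ≈ 650 per arm. The d detectable with 95% power at 20 per arm is 1.17. For 20 pairs, power at 0.2 SD of change is 14%, and 0.85 SD is detectable. A value near 0.2 does appear as Cohen's f (0.21 to 0.19) for a group-by-time interaction with 6 to 8 measurements and correlation 0.5. That is f rather than d, the inputs are not stated, and they fit neither 1a (two 12-hour levels per dose, one arm) nor the cognitive tasks (two visits).

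**2. Hypothesis 1a, one dose.** Paired t-test on log levels, n = 20. SD of the log change = √(2 ln(1 + CV²)); standardised change = ln(1.25)/SD, with ln(1.25) = 0.223; 90% CI factor = exp(1.729 × SD/√20).

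| Assumed CV | SD of log change | Standardised change | Missed, two-sided 5% | Missed, one-sided 5% | 90% CI: ratio × or ÷ |
|---|---|---|---|---|---|
| 30% | 0.415 | 0.537 | 37% | 25% | 1.17 |
| 50% | 0.668 | 0.334 | 71% | 58% | 1.29 |
| 80% | 0.995 | 0.224 | 84% | 75% | 1.47 |

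At CV 50%, an observed ratio of exactly 1 would still carry a 90% CI of about 0.77 to 1.29.

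**3. Hypothesis 1c, scores.** One score at one visit, 20 per arm, d = 0.5: noncentrality = 0.5 × √10 = 1.58 against a critical value of 2.02. The effect is missed 66% of the time two-sided and 54% one-sided. The 90% CI half-width is 1.686 × √(2/20) = 0.53 SD. Averaging T3 and T6 gives an effective d = 0.5/√((1 + ρ)/2) = 0.577 (ρ = 0.5) or 0.542 (ρ = 0.7), missed 57% or 61% of the time two-sided.

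**4. Hypothesis 1c, sobriety passes at one visit.** Newcombe 90% CI for the difference in proportions, CBD minus placebo:
- 20/20 against 20/20: 0, from -12 to +12 points.
- 18/20 against 20/20: -10, from -26 to +4 points.

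Losing non-completers widens all of these. At 16 per arm the half-width in step 3 becomes 0.60 SD.

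**The case against.** The strongest reply is that the plan is already largely descriptive. It presents means, SDs and counts, and a reader can derive a raw-scale interval for 1a from the SD of change and n. The mixed models can yield intervals, transformations are foreseen in 21.3.1, and the formal SAP is still to be written. Sobriety has a standard for each participant: "participants will not be permitted to leave the study site until they are able to pass a standard field sobriety test". The adverse event form also records clinical significance.

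Much of this stands. It makes the point a gap to close in the SAP, not a flaw in the design. It does not remove the gap: no interval is planned, the participant-level standards do not say what a group difference in scores means, and 21.3.4 still decides on accumulation from a mean and an SD.

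A second reply is that 95% power at d of about 0.2 would make a null result informative. The figure does not follow from the stated inputs (step 1). Even a correct power statement is not a criterion for concluding that there is no difference.

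A reader might also infer that the plan will treat p > 0.05 as proof of stability or safety. No section says so; the documents are silent on how a null result is to be read.

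**Conclusion.** The point holds as a minor-to-moderate analysis improvement. 1a and the psychomotor and cognitive part of 1c are no-difference predictions, and at 20 per arm or fewer neither a non-significant result nor a small mean change supports them without an interval. The size depends on the assumed 25% rise, CVs, d = 0.5 and visit correlations, none of which the protocol supplies. One-sided testing, or averaging the two cognitive visits, lowers the miss rates but does not make a null result informative.

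Some readers might go further and ask for a formal equivalence test, a larger sample or a change to 21.3.8. The documents do not support that: this is a 40-person proof-of-concept study, for which labelled estimates with intervals are enough. The point does not extend to 1b, which has a stated range of 200-400 ng/ml, or to the serious adverse event part of 1c.

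**What to change.** In 21.3.2 and 21.3.4, or in the pending SAP, before unblinding:

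1. **1a.** Beside the planned mean and SD of change, report the week-4 to week-1 geometric mean ratio of 12-hour CBD in the CBD arm (T4/T3 and T7/T6) with a 90% CI.
2. **1c.** Report the model-based CBD-placebo difference with a 90% CI for each cognitive score averaged over T3 and T6, and for each psychomotor score averaged over on-treatment visits. T8 is excluded because it falls after dosing ends. Per-visit estimates are supplementary. Report the difference in sobriety pass proportions at T1 and at T4 with a 90% CI.
3. **Reading.** State that p > 0.05 or a small mean change does not by itself confirm 1a or 1c, and label both as descriptive estimates with intervals. A margin fixed by the sponsor before unblinding is optional.

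The 90% level is chosen because the worry is directional (accumulation, impairment): it gives a one-sided 5% limit on the side of concern.

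**Cost.** Wording only; the measurements are already scheduled. The log ratio needs a rule for values below quantification. The intervals will be wide. Some will exclude zero by chance: with the seven cognitive tasks in 5.1.1, one averaged score each, about 7 × 0.10 = 0.7 would be expected to do so if there were no effect. They should be read as estimates, not tests.

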21.3.2 Analysis of the Primary Endpoint(s)

For Hypothesis 1a, acute circulating levels of CBD will be assessed in CBD-treated participants 45 minutes after initial administration (T1, T4), and 45 minutes after administration of the morning dose of medication following 1 day (T2, T5), 1 week (T3, T6), and 4 weeks (T4, T7) of treatment with each dose of CBD. Additionally, circulating levels of CBD will be assessed in CBD-treated participants 12 hours after ingestion of the preceding evening dose following 1 week (T3, T6) and 4 weeks (T4, T7) of administration of each dose of CBD. Levels of CBD (mean and standard deviation) will be reported at each timepoint and effects of dose and timepoint will be evaluated. For Hypothesis 1b, circulating CBD levels (mean and standard deviation) 45 minutes after administration of the morning dose of medication following 1 week (T3, T6) and 4 weeks (T4, T7) of treatment with each dose of CBD will be reported in CBD-treated participants. For Hypothesis 1c, between-group differences on psychomotor tasks (T1-T8), cognitive measures (T3, T6) and number of adverse events (T1-T9) will be assessed.

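### The T1 and T4 motor-safety count accepts any field sobriety pass within 2 hours of dosing, with no fixed test time or scored attempt, so impairment that clears inside the window can go uncounted

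*Combined protocol and SAP*

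**What the plan says.** Section 21.3.4 defines the acute motor-safety summary as "The number of participants within each treatment group that were able to pass a battery of psychomotor field sobriety tasks", with the limit "within 2 hours of the initial administration of each dose of CBD vs. placebo (T1 and T4"). The result "will be analyzed as summary statistics during treatment". No test, margin or expected pass rate is attached to it.

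Section 7.3.1 (Administration of Intervention) uses the same five tasks to decide when a participant may go home. Participants are to "remain at the study site with a study team member for approximately 2 hours following the initial administration" of each dose level, and "participants will not be permitted to leave the study site until they are able to pass a standard field sobriety test". The condition for dispensing the take-home supply is that "participants are able to pass field sobriety tests 2-3 hours after study drug administration".

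The hypothesis served is 1c in section 21.2, which begins "No clinically significant cognitive or motoric impairments" and is part of the primary objective in section 4.1. Its analysis in section 21.3.2 is that "between-group differences on psychomotor tasks (T1-T8), cognitive measures (T3, T6) and number of adverse events (T1-T9) will be assessed".

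None of these sections states how many times the battery is given after a dose, at what minute, what constitutes a pass, or which attempt enters the analysis. The acute blood samples, by contrast, are fixed at 45 minutes after dosing.

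**The concern.** A count of participants who managed a pass at some point before a deadline is an any-pass score. It can hide impairment in two ways. A participant may fail, be retested and pass before 2 hours. Or a participant may pass soon after dosing, before the drug has had its effect, and meet the definition whatever happens later in the window. Both are recorded exactly as someone who was never impaired.

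The release rule makes the first route plausible, because anyone who fails must be tested again before leaving and no limit on attempts is given.

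T1 and T4 are the supervised first administrations of each dose level, where acute motor effects are most directly observed. Hypothesis 1c predicts no clinically significant impairment, so a score that drops failures leans towards the predicted result.

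**Working it through.** **Step 1. How different courses are scored.** Reading sections 21.3.4 and 7.3.1 side by side:

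| Course after the first dose | Counted as a pass in 21.3.4? | Released under 7.3.1? |
|---|---|---|
| Never impaired, tested within 2 h | Yes | Yes |
| Fails, then passes before 2 h | Yes | Yes |
| Passes early, impaired later, clear by release | Yes | Yes |
| Fails up to 2 h, first passes at 2-3 h | No | Yes |
| Tested only at 2-3 h and passes | Not defined | Yes |

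Rows 2 and 3 are the defect. Row 4 shows that the 2-hour limit keeps longer impairment visible. Row 5 shows that the windows do not fit together: a participant whose only battery is the release check has no result inside the window being analysed.

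**Step 2. Size of the masking.** The plan gives no figure for this count, so there is nothing to reproduce. Inputs from the documents: 40 randomized 1:1, hence 20 per arm (section 5.1), and alpha 0.05 (section 21.4; taken as two-sided because sidedness is not stated). Assumed: the pass rate p on a single attempt, the number of attempts k inside the window, and independence between attempts. Then

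P(counted as a pass) = 1 - (1 - p)^k.

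With p = 0.95 on placebo and 0.60 on CBD:

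- k = 1: 20 x 0.95 = 19.0 against 20 x 0.60 = 12.0.
- k = 2: 1 - 0.05^2 = 0.9975 and 1 - 0.40^2 = 0.84, so 19.95 against 16.8.
- k = 3: 0.9999 and 1 - 0.40^3 = 0.936, so 20.0 against 18.7.
- k = 4: 1.0 and 1 - 0.40^4 = 0.9744, so 20.0 against 19.5.

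The plan only describes the count. As a yardstick for how well it separates the arms, the exact power of a two-sided Fisher test, with placebo at 0.95 per attempt throughout, is:

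| CBD pass rate per attempt | k = 1 | k = 2 | k = 3 | k = 4 |
|---|---|---|---|---|
| 0.80 | 16.8% | 0.1% | <0.05% | <0.05% |
| 0.60 | 71.6% | 19.7% | 0.7% | <0.05% |
| 0.50 | 89.4% | 56.7% | 9.5% | 0.7% |
| 0.30 | 99.7% | 98.9% | 86.8% | 54.4% |

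Masking is heavy for mild or moderate impairment with retests, and modest for severe impairment.

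**Step 3. Impairment that outlasts the window.** Assume an unimpaired participant passes with probability 0.98, and a fraction q of the CBD arm stays impaired throughout the 2 hours and does not pass. Expected passes are 20 x 0.98 x (1 - q) on CBD, against 19.6 on placebo:

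- q = 0.10: 17.6 (power 5.4%).
- q = 0.25: 14.7 (power 50.5%).
- q = 0.40: 11.8 (power 87.9%).

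The count can therefore still show a difference when impairment persists.

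**The case against.** A reader might infer something stronger: that because nobody leaves before passing, failed attempts disappear and both arms finish near 100% even if CBD impairs. The documents do not support that. The count stops at 2 hours, while the release check is described at 2-3 hours. A first pass after 2 hours releases the participant without making them a counted pass. Nothing says that failures go unrecorded.

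Three further objections deserve weight.

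- The number of attempts is assumed. One battery per visit within 2 hours fits section 21.3.4 equally well; the fail-then-pass route then disappears, though a single early test could still precede onset. Attempts made minutes apart by the same person are also likely to be correlated, which weakens the masking towards the k = 1 column. This stands, and it is why the figures are illustrations.
- Motor function is also compared between arms at T1-T8 under Hypothesis 1c, so this count is not the only motor result. That stands, but section 21.3.2 does not define the score. The motor tests listed in sections 5.1.1 and 8.1 are the same battery, so at T1 and T4 the comparison appears to inherit the same gap.
- Hypothesis 1c concerns clinically significant impairment, and a brief deficit that clears under supervision may not qualify. That is a fair clinical judgement, but it should be made on reported failures rather than settled by a scoring rule that omits them.

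**Conclusion.** The defect holds in a limited form. As worded, the section 21.3.4 count treats impairment that begins and clears within 2 hours of the dose as no impairment, because it sets a deadline but neither a test time nor a scored attempt. The direction favours the predicted null. The count remains informative for impairment lasting beyond 2 hours, so it is wrong to conclude that it cannot discriminate at all or that it supports Hypothesis 1c whatever the drug does.

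The size cannot be fixed from the documents. Under the assumed rates of 0.95 and 0.60, the expected gap shrinks from 7.0 participants per 20 with one scored attempt to about 3.2 with two attempts and 1.3 with three. It shrinks less if attempts are correlated, and retesting removes nothing if there is only one attempt. Separately, the windows in sections 21.3.4 and 7.3.1 differ and must be reconciled.

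**What to change.** In section 21.3.4, or in the formal SAP that section 21.1 promises before database lock and unblinding:

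- Name one post-dose attempt at T1 and at T4, at a fixed nominal time that is the same for everyone, and state the pass criterion. Count a failure on it as impairment even if a later attempt is passed.
- Report by arm the number failing that attempt and the number failing any attempt, including the release check, each with an exact 95% confidence interval for the CBD-minus-placebo difference. Report time to first pass by arm. The any-attempt figure matters because a single fixed time can miss later onset.
- Use the same score at T1 and T4 in the Hypothesis 1c psychomotor comparison in section 21.3.2.
- State how the 2-hour analysis window relates to the 2-3 hour release check. Leave the release rule itself unchanged.

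The cost is SAP wording plus recording the clock time and result of every attempt. If testing within the window is not already standardised, one timed battery must be scheduled at two visits where participants are on site for about 2 hours anyway. The reported pass rate may look slightly less favourable.
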